7.1 Statement of design

This is a two-stage feasibility study with a parallel qualitative study.

STAGE 1: a cohort study

STAGE 2: a placebo-controlled feasibility randomised controlled trial

Parallel qualitative study: using interviews and/or focus groups at three stages:

- Before start of study
- After Stage 1
- After Stage 2

7.2 Number of Centres

This trial will be conducted in a minimum of one institution in the UK, run at Cambridge University Hospitals NHS Foundation Trust. Our preliminary data has shown steady recruitment and retention longitudinally at one site (Cambridge University Hospitals NHS Trust) in the CogENT study.

7.3 Number of Patients

We plan to include a total of approximately 60 patients in this study. Up to 10 patients will take part in interviews prior to Stage 1, approximately 10 in Stage 1 and 38 in Stage 2 (randomised 1:1; 19 receiving the active FACES intervention and 19 receiving the control intervention.)

We will also be inviting patient's carers to take part in interviews/focus groups and to complete a caregiver Quality of Life form forms in Stage 1 and Stage 2.

Separate information sheets and consent forms will be provided for carers.

7.4 Participants Study duration

Patients will participate in the study until the post intervention study assessments which will be performed prior to commencing radiotherapy (approximately six weeks following surgery).

7.5 Study objectives

This is a feasibility study and as such our objectives relate to feasibility.

7.5.1 Stage 1: the cohort study

The specific objectives for this part of the study are:

- 1. To examine if patients are able to complete the intervention with the support of a psychologist (defined as completing all 9 sessions of training).
- 2. To study, document and understand the iterative changes of a new technique for delivering a rehabilitation intervention (FACES - computer based training programme) and provide a narrative account of these changes until a stable technique has been developed (as described for Stage 2a IDEAL interventions¹⁸).
- 3. To assess acceptability of intervention as part of the parallel qualitative study.

- 4. Feasibility of assessment completion by recording established validated outcome assessments patients are able to complete
- 5. Feasibility of quality of life completion by both patient and carer

7.5.2 Stage 2: placebo-controlled feasibility randomised controlled trial The specific feasibility objectives for this stage will be:

- 1. To explore if we are able to screen patients for deficits in emotional recognition using OCS-Bridge (https://ocs-bridge.com/about). This is a tablet-based neuropsychological screening tool that uses three sets of tests (a) the Oxford Cognitive Screen (OCS) that assess language, semantics, orientation, reading, movement, number knowledge, mental flexibility, spatial attention and memory. (b) the Cambridge Attention, Memory and Perception Screen, and (c) standardised tests of mood (PHQ-9 and GAD-7)
- 2. To assess acceptability of the intervention, based on patients meeting the eligibility criteria that give consent for the study. This will be explored further as part of the parallel qualitative study.
- 3. To assess the ability to complete the active FACES intervention and control intervention.
- 4. To assess the acceptability of a number of established, validated outcome assessments as part of the parallel qualitative study.
- 5. To assess the impact on patient reported quality of life.
- 6. To assess the impact on patient's families.
- 7. To compare the impact of the active FACES intervention with the control intervention on scores for selected assessments.

Parallel Qualitative Study

Using interviews and/or focus groups involving both patients and their carers. Participation in the qualitative study is optional for both patients and their carers. Separate participant information and consent forms will be used. A patient may take part without their carers participation at any stage of this study. A carer may take part without the participation of the patient for the initial interviews/focus groups before stage 1 (preintervention) only.

The objectives for this parallel study running through both stages of the study are:

- 1. To explore the experiences and perspectives of people with tumour, and carers regarding their lived experience and the perceived importance of the proposed intervention.
- 2. To explore their experiences of the intervention including preferred/suitable intervention content and delivery formats, experience of randomisation and potential barriers and facilitators to intervention delivery.
- 3. Perceptions of outcome measures and whether they capture the issues of importance to people completing the intervention.

4. To explore the experiences and perspectives of health care professionals regarding their experiences of delivering the intervention and potential barriers and facilitators to further delivery of the intervention within routine clinical services.

7.6 Study Outcome Measures

7.6.1 Stage 1: the cohort study

The specific outcome measures for this part of the study are:

- 1. Percentage of patients completing the intervention (defined as completing all 9 sessions).
- 2. Prospective recording of any changes to the administration, conduct and content of the rehabilitation intervention on a patient-by-patient basis.
- 3. The acceptability of the intervention will be explored through a parallel qualitative study (see below 7.6.3).
- 4. Percentage of patients completing the following validated outcome assessments
 - a. Diagnostic Assessment of Non-verbal Accuracy-2, Adult Faces (DANVA2-AF);
 - b. Emotion Recognition and Social Inference: The Awareness of Social Inference Test (TASIT), (part 1, EET subtest);
 - c. The Toronto Alexithymia Scale-20 (TAS-20).
- Percentage of patients and carers able to complete quality of life questionnaires.

7.6.2 Stage 2: placebo-controlled feasibility randomised controlled trial The outcome measures for this stage will be:

- 1. We will record the number of patients who undergo screening (the numerator) and the number of potentially eligible patients that attend clinic (the denominator). To proceed with a larger, efficacy study we would need to be able to use OCS-Bridge to screen a minimum of 75% of new patients.
- The percentage of screened patients meeting the eligibility criteria provide informed consent for the study. It will also be explored in more detail with the qualitative study (see below).
- 3. Percentage of patients who have completed all sessions for the FACES intervention (active intervention) and General Cognition Intervention (control intervention). To proceed to further studies this will again need to exceed 80%.
- 4. We will measure completion rates for the following established, validated outcome assessments pre- and post-intervention.
 - a. Diagnostic Assessment of Non-verbal Accuracy-2, Adult Faces (DANVA2-AF);
 - b. Part 1, which includes emotion recognition, of Emotion Recognition and Social Inference: The Awareness of Social Inference Test (TASIT);
 - c. The Toronto Alexithymia Scale-20 (TAS-20).

Acceptability will be explored with our parallel qualitative study.

- 5. Patient reported quality of life using the EORTC QLQ-30 with the BN20 brain tumour module¹⁹.
- 6. The impact of these problems on patient's families by asking interested family members to complete the Caregiver Quality of Life Index-Cancer (CQOLC).
- 7. We will calculate the difference in scores pre and post intervention for the selected assessments (see above) for both the active (FACES) intervention group and the control group. This will provide an early indicator that the intervention may make some difference and would be worth exploring in a larger, multicentre study as well as determining future sample sizes.

7.6.3 Parallel Qualitative Study

Using interviews and/or focus groups with both patients and their carers. Three time points will be studied – for each time point specific questions will be explored:

- 1. Before start of stage 1: we will involve patients that would be eligible to participate in stage 1 of the study and their carers. We will explore the following topics:
 - a. What is the patient's and their family's lived experience of coping with tumour and disorders of social cognition?
 - b. What do the potential participants feel about the proposed study what potential barriers and enablers to trial participation can they see. This will be used to optimise the intervention before Stage 1.
- 2. After Stage 1: we will involve the patient group recruited to Stage 1 of the study and their carers. We will explore:
 - a. Experiences of being involved in the study and study interventions?
 - b. How we may improve delivery of interventions and assessments?
 - c. How will we approach future patients to Stage 2 and discuss randomisation?
- 3. After Stage 2: we will involve patients recruited in Stage 2 of the study and their carers. We will explore:
 - a. How can we improve delivery of this intervention to routine clinical practice to maximise its acceptability to patients?
 - b. What changes would we need to implement in a larger Phase III trial?
 - c. How do the outcome measures reflect patient experience is there a discrepancy between changes in outcome measures and what patients experience?

Participation in the qualitative study is optional for both patients and their carers. A patient may take part without their carers participation at any stage of this study. A carer may take part without the participation of the patient for the initial interviews/focus groups before stage 1 (pre-intervention) only. Separate information sheets and consent forms will be provided.

Selection and withdrawal of subjects

8.1 Inclusion Criteria

Patients recruited to this study will require the following inclusion criteria:

- 1. Patients pre-screened as part of the CogENT and SIND studies, scoring 11 or less on the emotional recognition test within the OCS-Bridge screening tool done pre-operatively (consistent with having a deficit pre-operatively)
- 2. Signed Informed Consent to SCARF-BT study
- 3. Aged 18 years and older
- 4. Imaging evidence of a high-grade glioma as assessed by a neuro-oncology MDT;
- 5. MDT and treating clinician recommend either biopsy or debulking of the tumour;
- 6. Patients scoring 11 or less on the emotional recognition test within the OCS-Bridge screening tool done post-operatively (consistent with having a deficit post-operatively)
- 7. Patients with WHO Performance status 0-2;
- 8. Patients suitable for oncological intervention (involving radiotherapy/ chemotherapy/ combining radiotherapy and chemotherapy);
- 9. For Qualitative Study only: speaks fluent English as the use of interpreters can alter patients exact words.
- 10. For Qualitative Study only: willing to participate in interviews and/or focus groups.

11.

8.2 Exclusion Criteria

The presence of any of the following will preclude patient inclusion:

- 1. Patients unable to give written consent or who lack capacity to consent;
- 2. Patients for palliative/best supportive care only, following surgery.
- 3. Pre-morbid developmental or acquired/traumatic neurologic disorder (e.g. autism, stroke, severe head injury or dementia/cognitive impairment);
- 4. Pre-morbid major psychiatric disorder (e.g., schizophrenia);
- 5. Impaired vision and/or hearing that would interfere with task participation (determined by interacting with participant on screening and medical history);
- 6. Impaired facial recognition (i.e. prosopagnosia) using a separate test from the OCS-Bridge screening tool, where a score of ≤5 on immediate assessment of neutral face recognition would suggest a deficit requiring exclusion.

8.3 Inclusion Criteria for Carers

- 1. Written informed consent
- 2. Family member/someone they care for with Brain Tumour who is participating in this study
- 3. Able and willing to complete the caregiver Quality of Life guestionnaire

SCARF-BT Protocol IRAS: 270758 Version Number: 1.1

- 4. For Qualitative Study only: speaks fluent English as the use of interpreters can alter patients exact words.
- 5. For Qualitative Study only: willing to participate in interviews and/or focus aroups.

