9.1 Patient identification

Patients that will be approached for this study will have already been recruited for one of the two studies detailed below. They will have had a cognitive screen using the OCS-Bridge screening battery as part of either:

- 1. The Cognition Evaluation for patients with Neurological Tumours (the CogENT study) - REC reference: 18/LO/0491.
- 2. Assessing impact of surgically-induced deficits on patient functioning and quality of life (SIND study) - REC reference: 19/WM/0152.

Patients will be identified pre and post operatively from our Multi-Disciplinary Team (MDT) process.

It is important to identify patients with pre-existing defects of emotional recognition preoperatively as a further 20% of patients acquire temporary deficits post-operatively. Whereas our data from the CogENT study suggests patients with deficits pre-operatively do not improve at delayed assessment. This method of identifying potential patients will therefore help exclude patients that may get better without any rehabilitation. Patients scoring 11 or less on the emotional recognition test that are part of the OCS-Bridge battery are considered to have a deficit.

Patients will be approached either in a clinic or remotely by telephone (in accordance with Trust guidance concerning COVID-19). The study will be introduced to the patient and they will be provided with the patient information sheet. Patients will be given time to think about participating and will be followed up by phone call/further phone call. Patients who wish to take part will then be invited to give written consent at their next clinic visit. The patient's carers will also be approached about completing their own assessments. Carers who wish to take part will give written informed consent.

SCARF-BT Protocol IRAS: 270758 Version Number: 1.1

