9.7 Study Assessments - Post-Intervention

These assessments will be performed before the start of radiotherapy and after completing the three weeks of the intervention. Time points later than this will be confounded by effects of radiotherapy. These assessments will include:

- Diagnostic Assessment of Non-verbal Accuracy-2, Adult Faces (DANVA2-AF);
- 2. Part 1 (EET subtest) of Emotion Recognition and Social Inference (TASIT);
- 3. The Toronto Alexithymia Scale-20 (TAS-20).
- 4. Patient reported quality of life. (EORTC QCQ30 with the BN20)
- 5. Patient's families quality of life.(Caregiver Quality of Life Index-Cancer (CQOLC). http://www.midss.org/content/caregiver-quality-life-index-cancer-cgolc-scale

Quality of life questionnaires will be completed before the clinic visit. If patients or their carers become distressed by the topics raised in the quality of life questionnaires, they will be supported by members of the clinical research team during their clinic visit.

Stage 1 will be used to define which of the assessments that patients are able to complete. These assessments will be used for stage 2.

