11.2 Statistical methods

11.2.1 Stage 1- Criteria for Stop/Go decision prior to Stage 2

At the end of Stage 1 there will be an assessment made by the SMG as to whether the Stage 2 study should go ahead. This decision will be made on the following criteria:

- 1. Percentage of patients attending the Surgical Neuro-oncology Clinic that are screened for emotional recognition deficits pre-operatively?
- 2. Percentage of patients with a deficit that are approached for the study?
- 3. Percentage of patients recruited that can complete all the assessments?
- 4. Percentage patients recruited that are able to complete the FACES intervention adapted for remote delivery with the assistance of a psychologist.

As per the sample size calculations described above, less than 50% would be deemed unacceptable (see Sample Size calculation above).

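### Stage 1 carer completion, taken among enrolled carers, is biased upward because carers enter only if able and willing to complete the form

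*Protocol*

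**What the plan says.** Stage 1 objective 5 (Protocol 7.5.1) is "Feasibility of quality of life completion by both patient and carer". The matching outcome, item 5 in 7.6.1, is the "Percentage of patients and carers able to complete quality of life questionnaires". It states no denominator and no threshold.

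Carer criterion 3 in 8.3, repeated in the synopsis, admits a carer who is "Able and willing to complete the caregiver Quality of Life" questionnaire. Section 9.1 adds voluntary consent: "Carers who wish to take part will give written informed consent".

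The caregiver form (CQOLC) is due at baseline (9.4) and again post-intervention (9.7). On the second occasion, "These assessments will be performed before the start of radiotherapy and after completing the three weeks of the intervention".

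In Stage 2, item 6 of 7.6.2 measures the effect on families "by asking interested family members to complete the Caregiver Quality of Life Index-Cancer (CQOLC"). It is an impact measure and not a completion rate. The third stop/go criterion in 11.2.1 is the "Percentage of patients recruited that can complete all the assessments"; carers are not mentioned.

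**The concern.** The carer entry rule and the Stage 1 carer outcome ask almost the same question. A carer who cannot or will not complete the questionnaire is not enrolled, and so never appears as a non-completer.

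A later trial that wants a caregiver outcome needs to know what share of its patients will yield usable CQOLC data. A percentage among enrolled carers cannot show this. It would be the same whether nearly every approached carer joined or only a minority did. If it were read as the answer to objective 5, it would make the caregiver measure look easier to collect than it is. That matters because CQOLC is the only quantitative measure the Protocol attaches to the Stage 2 objective on patients' families.

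**Working it through.** The Protocol states no carer completion figure, so there is nothing to reproduce. The check compares the sections and then illustrates the structure with assumed values.

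**Comparison of sections**

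- *Carers.* Entry (8.3, criterion 3) requires ability and willingness to complete the form. The outcome (7.6.1, item 5) is ability to complete it. The Protocol describes no count of carers identified, approached, declining or unable.
- *Patients.* The list in 8.1 opens with "Patients recruited to this study will require the following inclusion criteria", and neither it nor 8.2 requires ability to complete the quality-of-life forms. The circularity therefore concerns carers only.
- *Recruitment counts for patients.* In 7.6.2, item 1 defines a numerator and denominator for screening, and item 2 makes consent among eligible patients a separate outcome. Carers have no equivalent.

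**Illustration**

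Let *w* be the share of approached carers who are able, willing and consent. Let *c* be the share of enrolled carers who complete the form. The Protocol gives neither, so both are assumptions.

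- Rate among enrolled carers = *c*
- Rate among approached carers = *w* × *c*
- Ratio of the two = 1/*w*

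| *w* | *c* | Among enrolled | Among approached |
|---|---|---|---|
| 0.4 | 0.70 | 70% | 28% |
| 0.6 | 0.85 | 85% | 51% |
| 0.8 | 0.85 | 85% | 68% |
| 1.0 | 0.85 | 85% | 85% |
| 0.6 | 1.00 | 100% | 60% |
| 1.0 | 1.00 | 100% | 100% |

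The three rows with *c* = 0.85 make the point: the enrolled-carer figure stays at 85% while the approached-carer figure runs from 51% to 85%. Over *w* = 0.4 to 1.0 and *c* = 0.70 to 1.00, the first ranges from 70% to 100% and the second from 28% to 100%. The ratio 1/*w* ranges from 1/0.4 = 2.5 down to 1.

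If each registered patient has exactly one approached carer, the approached-carer column is also the rate over registered patients. If some patients have no carer, the all-patient rate is lower still.

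**Precision**

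Stage 1 recruits up to 10 patients. Assuming one carer each and 10 of 10 completing, the exact (Clopper-Pearson) 95% lower limit is 0.025^(1/10) = 0.69, giving an interval of 69% to 100%. If 6 carers enrolled and all 6 completed, the lower limit is 0.025^(1/6) = 0.54, giving 54% to 100%. The estimate is imprecise under any denominator, and the selection adds bias to that imprecision.

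**The case against.** Several points on the other side stand.

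- **A reader might infer that the percentage must be close to 100%, or that it says nothing about feasibility.** The Protocol supports neither. Criterion 3 is judged at entry, and CQOLC is repeated after three weeks of intervention, so an enrolled carer can still fail to return a form or drop out. Completion and retention among consenting carers is a legitimate feasibility quantity, though not the whole of objective 5.
- **The denominator is unstated, and such detail is often left to the SAP.** If all approached carers were counted, the bias would largely disappear. But the entry rule is fixed in the Protocol, and enrolled carers are the natural reading. An SAP could divide CQOLC forms by registered patients; it could not recover uptake or reasons for refusal that were never recorded.
- **A reader might extend the point to Stage 2 or to the stop/go decision.** Stage 2 completion rates are planned only for DANVA2-AF, TASIT and TAS-20, and item 6 is an impact measure. Inviting interested relatives is ordinary voluntary recruitment. The stop/go criteria count patients and set no carer threshold.
- **Deleting criterion 3 would not cure the problem.** This is right: carers must still consent, so unwilling carers would remain outside.
- **An all-patient denominator mixes carer availability with form completion.** This is a fair objection to using it alone. It is answered by reporting the components beside it.

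**Conclusion.** The point holds for Stage 1 carers. Criterion 3 screens on the property that outcome 5 measures, so a percentage among enrolled carers is biased upward for objective 5 and is insensitive to uptake. It still describes completion and retention among volunteers at baseline and post-intervention.

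The direction of the bias follows from the text, on the reading that enrolled carers form the denominator. Its size does not: every percentage in the illustration rests on assumed uptake and completion, and the bias would vanish if uptake were complete. No carer threshold, stop/go rule or Stage 2 completion outcome depends on the figure. The change is worth making because it is cheap and lets a named feasibility objective be answered.

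**What to change.** In 7.6.1 item 5, plan a log for each registered patient showing whether a carer was identified, approached, consented, or declined or was unable. Report:

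- (a) patients with CQOLC completed at each time point, divided by all registered patients;
- (b) uptake among carers approached;
- (c) completion among consenting carers at each time point.

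State that carers failing criterion 3 count as non-completers in (a). Criterion 3 can then stay as it is.

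For 7.6.2 item 6, report the number of registered patients with CQOLC data beside the impact result. This adds context and does not create a new completion outcome.

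The cost is the wording change, one log item per patient, and a headline percentage that will probably look less favourable. No clinical procedure changes.

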8.4 Subject withdrawal criteria

Patients may withdraw from the trial assessments or from the trial completely, at any time at their own request, or they may be withdrawn at any time at the discretion of the Investigator or Sponsor for safety, behavioural, or administrative reasons.

If the patient withdraws consent for disclosure of future information, no further evaluations should be performed and no additional data should be collected. The Study Management Group (SMG) may retain and continue to use any data collected before such withdrawal of consent.

Patients should be withdrawn from the study and replaced only if the patient requests to be withdrawn.

Procedures and assessments

Summary of the timings and assessments is listed below in the table - Section 9.9.

